## Development of the intervention

- The intervention of this study follows the intervention development by Schoeb et al. 2020.
- Feasibility assessment such as: availability of time and resources, recruitment of participants, methods of data collection, operating environment such as availability of facilities or equipment (MR glasses) and commitment of participants.
- To develop the NGT insertion material based on evidence-based nursing studies. The material is used for MR, video and instructor-led training.
- A pilot group (teachers and students) will test the intervention.

## Students baseline assessment (M0):

- Demographic information (students age, gender, education and use of previous device background)
- NGT theory pre-test
- Inclusion and exclusion criteria

Randomization according to intervention 1 (MR) group, intervention 2 (video) group and control (instructor) group

### Intervention group 1 (N=60):

- Mixed Reality Learning
- MR glasses technical training to students and teachers

### Intervention group 2 (N=60):

- Video-Based Learning
- Video systems technical training to students and teachers

### Control group (N=60):

- Instructor-led training
- Introduction of teachers to nasogastric tube insertion

## Students practice nasogastric tube insertion (followed by a teacher assistant)

- Intervention group 1 using MR glasses and virtual instructions
- Intervention group 2 using Video-Based instructions
- Control group practices using Instructor-led training

## Evaluation of intervention

Follow-up assessment after practice post-intervention (M1)

- System Usability Scale (SUS), User Experience Questionnaire (UEQ), NASA Task Load Index, NGT theory post-test
  - students answer after performance
  - Students reflection text (only MR group)
- Students move to another room and perform the NGT procedure without instruction.
  - A structured NGT checklist → assessed by research assistant or staff

Follow-up assessment six-month post-intervention (M2)

- Students perform NGT insertion again without instruction.
- A structured NGT checklist → assessed by research assistant or staff

Figure 1. intervention description

The sample size calculation is based on previous research by Schoeb et al., 2020. The calculation employs a delta value of 1,53 points, a standard deviation (SD) of 0,15 points, a type 1 error of 0.05, and a study power of 80%. The calculated sample size is 3 x 55 students, and the planned sample size is 3 x 60 students, based also on the Spring 2025 pilot, to account for potential attrition. A pilot data collection will take place in spring 2025, and the full data collection will occur from autumn 2025 to spring 2027. The detailed implementation of the study is described in the table below:

Paper I: Assess and comparing the learning outcomes of nursing students in NGT insertion using Mixed Reality Learning, Video-Based Learning and Instructor-led training - a research protocol for a randomized trial.
 
The research question: What kind of learning outcomes can be observed in nursing students in NGT insertion using Mixed Reality Learning, Video-Based Learning and Instructor-led training?
 
Article I: Assessing and comparing Mixed Reality Learning, Video-Based Learning and Instructor-led training in the context of performance in nasogastric tube insertion for nursing students: A randomized controlled study. Submission for autumn 2027.
			

Paper II: To assess and compare the MR technology and video usability.
 
Research question: How students experienced the usability of MR technology and video tools in learning how to insert a nasogastric tube.
 
Article II: Usability of MR and video technology in learning nursing skills in nursing education. Submission for spring 2027.
			

Paper III: Describing students' experiences of using Mixed Reality in nursing education.
 
The research question: What were the students' main experiences with using MR technology to practice nursing clinical skills?
 
Article III: Nursing students' experiences of Mixed Reality technology in clinical skills learning: A qualitative study. Submission to autumn 2026.
			
Population	Settings	Data collection	Analysis
First year nursing students (N=180).	Students practice NGT insertion into mannikin. The instructional material for all groups is the same included content from a technical and non-technical point of view. The only difference between the groups is the technology used to implement it.	
Students answer the questions (M0) about demographic information (students age, gender, educational background) and make NGT theory pre-test.
 
Students' clinical competence and performance assessed using an NGT checklist (primary endpoint). After the NGT was inserted, students answer NGT theory post-test (secondary dependent variable) and answer the questionnaires: System Usability Scale (SUS), User Experience Questionnaire (UEQ) and NASA Task Load Index. The SUS scale is five-point Likert scale (10 questions) and aims to determine which device, glasses or video was easier, more enjoyable, and more effective to use. Higher scores indicate better usability.
 
User Experience Questionnaire (UEQ) scales of the questionnaire cover a comprehensive impression of user experience. Both classical usability aspects (efficiency, perspicuity, dependability) and user experience aspects (originality, stimulation) are measured.
 
NASA Task Load Index (TLX) assesses workload on five 6-point scales, and it evaluates the mental workload and experiences of students while performing the task.
 
Students who use MR glasses send a written reflection after completing the procedure. Student experiences with MR glasses will be collected using a reflective learning journal rubric adapted from the model by Liu, Kitto & Shum (2021). Reflection text
	
Statistical analyses are performed using SPSS- software. Anova is used to compare the mean scores of the three groups on the total checklist scores and to assess which learning and teaching method influences students' NGT insertion learning outcomes. The P-value will be used to test whether the differences between the teaching methods are statistically significant. SUS and NASA TLX are analyzed with SPSS. Both video and glasses are given SUS and NASA TLX scores between 0-100. The value represents the level of usability and task workload. The results are analyzed with a T-test, which is a common method for comparing the means of two groups.
 
Student reflective analysis is an inductive approach using traditional content analysis of student written reports. Analyzed and coded using the software ATLAS.fi.
 
Statistical analysis will be ready spring 2027.


	
consisting open-ended questions in which students describe their learning process in their own words.
 
After six -month (M2) students perform NGT insertion again without instruction. Performance assessed NGT checklist.
	
--	---	--

Figure 2. implementation of the study

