### 3 Research implementation

The study will be conducted as a randomized controlled trial (RCT) with first-year nursing students in one University of Applied Sciences. In the first phase, the aim is to develop a Mixed Reality and Video- Based intervention utilizing the Medical Research Council (MRC) Framework. The MRC Framework serves as a guide for researchers in designing research projects and aids in the development and evaluation of complex interventions.

The MRC framework 2021 includes four phases of intervention: development or identification of the intervention, feasibility, evaluation, and implementation (Skivington et al., 2021). The students are randomized into three groups, intervention 1 (MR group), intervention 2 (video group), and control (Instructor-led) in a manner where the researcher has no influence on the allocation of the groups. Randomization is done using a computer program. The inclusion criteria are the following: the student is studying to become a nurse, student performing the NGT insertion procedure for the first time and had no theory or pre-material on the treatment procedure. Exclusion criteria include: the student has no previous nursing education (e.g. practice nurse), students have no epilepsy or the pacemaker.

In the second phase students answer questions about demographic information and answer a theoretical exam (pre-test) on nasogastric tube insertion to assess their baseline knowledge and skills. The pre-test is used to measure the homogeneity of the groups. Student performance is measured using a structured NGT checklist (primary endpoint). A structured NGT checklist are used to assess students' clinical competence and performance and based on a checklist to monitor how well students follow non-technical and technical procedural steps. (Kebede et. al 2024.)

After completion students answer the NGT theory post-test (secondary dependents). The usability of MR glasses and video is measured using The System Usability Scale (SUS) questionnaire (primary endpoint), secondary dependents are NASA's Task load index (TLX), User Experience Questionnaire (UEQ), and students' reflective text, where students describe their experiences with MR technology as teaching method and identify the factors that either facilitate or hinder the learning of nursing skills within an MR environment. The detailed description of the intervention:

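### The two M0 lists disagree on previous device use, and the valid t-test for SUS and NASA-TLX passes up a small, nearly free gain from adjusting for it

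*Protocol*

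**What the plan says.** The protocol describes the baseline data in three places.

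- Section 3, running text, gives no itemised list: "In the second phase students answer questions about demographic information and answer a theoretical exam (pre-test) on nasogastric tube insertion".
- Figure 1, in the box for the students' baseline assessment, which stands before the randomisation step, has four items: "Demographic information (students age, gender, education and use of previous device background".
- Figure 2, Data collection column, has three demographic items and the theory test: "Students answer the questions (M0) about demographic information (students age, gender, educational background) and make NGT theory pre-test".

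Only one baseline measure is given a purpose, the theory pre-test: "The pre-test is used to measure the homogeneity of the groups".

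On usability, section 3 states: "The usability of MR glasses and video is measured using The System Usability Scale (SUS) questionnaire (primary endpoint". NASA-TLX is secondary. Figure 2, Analysis column, scores both from 0 to 100 for video and glasses and then fixes the comparison: "The results are analyzed with a T-test, which is a common method for comparing the means of two groups". No covariate is named. On allocation, section 3 says: "Randomization is done using a computer program". Figure 1 plans 60 students for the MR group and 60 for the video group.

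**The concern.** The text that leads into Figure 2 presents it as the detailed account of how the study is carried out, and its demographic list is a closed parenthesis. According to section 5, the survey forms are built in REDCap. Someone building the M0 form from Figure 2 would have no prompt to include previous device use, whereas someone working from Figure 1 would.

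Of the four demographic items in Figure 1, device use is the only one that concerns technology. It is therefore a natural candidate to explain part of the spread in how usable students find MR glasses or video. Section 2 expects MR to score highest on usability, and SUS is the endpoint that will test this. An item collected before randomisation can be used safely as a covariate. If it is left off the form, or collected and not used, the MR-versus-video comparison forgoes whatever precision the item could have given, and any chance difference in experience between the arms stays in the estimate.

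**Working it through.** **1. The lists side by side**

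| Item at M0 | Section 3 text | Figure 1 | Figure 2 |
|---|---|---|---|
| Age | not itemised | yes | yes |
| Gender | not itemised | yes | yes |
| Education | not itemised | yes | yes |
| Previous device use | not itemised | yes | **no** |
| Theory pre-test | yes | yes | yes |

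The only difference between the figures is previous device use, and the running text does not settle which list applies.

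**2. Is the stated t-test valid?**

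Two arms of 60 were simulated with no true difference and a covariate correlated r with the outcome but ignored in the test (20,000 runs per value, nominal 5%). Rejection rates were 5.1% at r = 0, 5.0% at r = 0.3 and 5.1% at r = 0.5. The test keeps its level.

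**3. What adjustment would gain**

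Inputs: n = 60 per arm (Figure 1); two-sided alpha 0.05 and power 80% (the protocol gives 0.05 and 80%; two-sided is assumed). The correlation r between device experience and SUS is assumed, because the protocol gives none.

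- Share of residual variance removed: r².
- Equivalent size of an unadjusted arm: 60/(1 − r²).
- Detectable difference in SD units: (1.960 + 0.842) × √(2/60) × √(1 − r²) = 0.511 × √(1 − r²).
- Power at an assumed difference of 0.5 SD: Φ(0.5/[√(2/60) × √(1 − r²)] − 1.960).

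| Assumed r | Variance removed | Equivalent n per arm | Detectable difference (SD) | Power at 0.5 SD |
|---|---|---|---|---|
| 0 | 0% | 60 | 0.511 | 78.2% |
| 0.1 | 1% | 60/0.99 = 60.6 | 0.509 | 78.6% |
| 0.2 | 4% | 60/0.96 = 62.5 | 0.501 | 79.8% |
| 0.3 | 9% | 60/0.91 = 65.9 | 0.488 | 81.9% |
| 0.4 | 16% | 60/0.84 = 71.4 | 0.469 | 84.8% |

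**4. Chance imbalance**

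With 60 per arm, the standardised difference between arms in a baseline covariate has standard deviation √(2/60) = 0.183, so 95% of randomisations fall within ±1.96 × 0.183 = ±0.36 SD. Multiplied by r, the shift in the SUS contrast is at most about 0.36 × 0.2 = 0.07 SD, 0.36 × 0.3 = 0.11 SD or 0.36 × 0.4 = 0.14 SD in those 95%. The t-test's standard error already covers this variation; adjustment removes it.

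**5. Cost in degrees of freedom**

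A binary or linear covariate costs one degree of freedom; k categories cost k − 1. Against 120 students, either is negligible.

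**The case against.** The strongest reply is that the analysis contains no error. MR and video students are randomised, so a two-group t-test is unbiased, and the simulation shows that it keeps its 5% level. Chance imbalance is ordinary sampling variation, which the test allows for. Choosing covariates is also often left to a statistical analysis plan, and one may exist. All of this stands, and it limits the point to a gain in precision.

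A reader might infer more from the text in four ways, none of which the protocol supports.

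- *That the item will be lost.* Figure 1 explicitly asks for it, and nothing says which figure the form is built from. Omission is a risk.
- *That the item could not be recovered later.* Prior use is a historical fact that can still be asked. Answers given after a session with the glasses may be coloured by it, but the protocol offers no evidence either way.
- *That the item will go unused.* The protocol names the test for the group means. It does not rule out adjusted analyses elsewhere.
- *That device experience is the most important baseline predictor of usability.* This is plausible, but the protocol does not rank its baseline variables.

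Two further objections bear on the size of the gain. The literature review says MR devices are not yet in wide use, so few first-year students may have experience of them, and an item on which nearly everyone gives the same answer explains little. The item is also generic: experience with MR glasses might predict SUS for glasses but not for video, which would lower the overall correlation. Both stand as reasons to expect the lower end of the range, or nothing.

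What remains is that the two lists differ and that the stated method for a primary endpoint makes no use of a baseline item that Figure 1 already plans to collect.

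**Conclusion.** The point holds as a minor one in two parts. First, the M0 lists in Figures 1 and 2 contradict each other on previous device use and must be reconciled; this rests on the text alone. Second, the t-test for SUS and NASA-TLX is valid but gives up a modest amount of precision. At assumed correlations of 0.2 to 0.4, adjustment is worth about 62 to 71 students per arm instead of 60. At 0.3 the detectable difference moves only from 0.511 to 0.488 SD, and at 0.1 it hardly moves. Every correlation here is an assumption, as is the 0.5 SD difference used for power. The result should not be read as saying that the planned usability comparison is biased or that its p-value is wrong.

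**What to change.** 1. **Figure 2, Data collection column:** add previous device use to the M0 list so that it matches Figure 1, and check that the REDCap form contains it before randomisation. Define the item, preferably as a single yes/no question stating which devices count.

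2. **Figure 2, Analysis column:** analyse SUS and NASA-TLX each with a linear model containing group (MR versus video) and prior device experience as one covariate, prespecified before outcomes are compared (for example binary, costing one degree of freedom). Report the adjusted mean difference with its 95% CI. Keep the unadjusted t-test as a supporting analysis.

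The cost is one line in each column of Figure 2 and at most one question on an electronic form. No extra students, visits or measurements are needed, and the model can be fitted in SPSS, which the protocol already names. If almost no student reports prior experience, the adjusted and unadjusted results will nearly coincide and little has been spent.

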#### 4 Significance of the research

Future learning and the use of technology are developing rapidly both in nursing education and in working life, which is why research is topical from the perspective of both nursing science and education science. The study's purpose is to provide an understanding and knowledge of how MR learning can be used in the future as part of clinical skills learning for nursing students, as well as how usable current MR technology is in nursing education. In addition, the study anticipates the concrete benefits of the educational environment, such as the targeting of teachers and financial resources, considering the individual learning needs of students, and responding to the clinical competence of students also from the perspective of patient safety.

#### 5 Ethical considerations

Research complies with high-quality scientific practice and ethical activities in accordance with TENK's guidelines (TENK 2023.) Ethical approval was obtained prior to the start of the pilot, and research permission was granted by Turku University of Applied Sciences. Participants will receive comprehensive information about the research, emphasizing the voluntary nature of participation, and written consent will be sought. Participants will have the option to withdraw from the study at any point and it does not impact the progress or assessment of studies. To ensure anonymity, students will be assigned numerical identifiers, preventing identification from the results. Collected data will be stored on the researcher's computer with password protection. Research material will be retained for five years after the last article's publication, followed by proper destruction. The REDCAP software designed for sensitive data will be utilized for creating survey forms and collecting data.

#### 7 Financing plan

The study period is 8/2024- 7/2028. The study's costs are personnel costs, tools, statistician, translation fees and conference travel. The duration of the work will be occasional, approximately 20 hours/week. In addition to this, as a researcher, I am supposed to take research leave from my own work. There are various grants that I have planned to apply and some of them are interested in funding research about education: The Finnish Cultural Foundation, The Finnish Nurses Association, OKKA Foundation and Turku University Foundation.

